## 5.0 STUDY PLAN

## 5.1 Schema

After consent, study coordinator can request archival endometrial biopsy

Details of testing measurements are available in the Time and Events Table. The baseline testing visit can occur either at the clinic visit or the participant can return to the exercise physiology lab in Fetzer Hall. Subjects will receive instruction on their personalized HIIT intervention. The personalized HIIT intervention will be adjusted so the participants can complete 4-8 HIIT sessions, with 24 hours of rest time, prior to surgery.

Surgery will take place per SOC and will not be dictated by the study. Endometrial biopsy will take place after sedation by surgeon, hysterectomy specimen will be removed as part of SOC testing

Post-surgical testing and SOC post-surgical visit will take place 2-4 weeks after SOC surgery. The VO2 peak testing is optional at this visit.

This project is a phase 0 clinical trial in which all patients who undergo surgical staging for EC will participate in the HIIT intervention group that will complete 4 to 8 sessions of home-based HIIT prior to hysterectomy. The effect of HIIT on proliferation and apoptosis will be compared between pre-intervention endometrial biopsies and post-intervention endometrial tissue/hysterectomy specimens. Expression of regulators of insulin/IGF-1/fatty acid/lipid synthesis pathways will be compared pre- and post-HIIT intervention in ECs.

Based on our preliminary data, HIIT should rapidly lead to improvements in cardiometabolic health in EC patients within 4 to 8 sessions (approximately 2-3 wks of HIIT). To assess the benefits of HIIT in EC, we propose a comprehensive assessment of

cardiovascular and metabolic biomarkers of HIIT response among women enrolled in this phase 0 study that includes traditional (VO2peak, BMI, HgBA1C) and novel (metabolomic profiling) assessments of obesity/overweight, insulin resistance, and cardiorespiratory fitness.

We predict that the HIIT intervention will result in decreased proliferation and increased apoptosis when comparing tumors pre- and post-HIIT. Based on our experience with this HIIT protocol in various special populations, EC patients are anticipated to demonstrate good compliance and report sufficient tolerability to the intervention. In addition, we anticipate that hyperactivation of the insulin/IGF-1/AMPK/mTOR pathway and stimulation of fatty acid/lipid biosynthetic pathways will be found in the endometrial tumors pre-HIIT, and HIIT therapy will result in inhibition of downstream targets of these metabolic pathways. Moreover, we expect BMI, waist-to-hip ratio, and HgBA1C to decrease. Elevated pre-treatment serum levels of fatty acids and glycolipids should be found in those obese/overweightwomen who best respond to HIIT, indicative of a more insulin-resistant metabolic phenotype in HIIT-responders. This insulin resistant metabolic profile should improve with HIIT treatment.

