## 2.0 STUDY OBJECTIVES

## 2.1 Primary Objective

**2.1.1** Determine the anti-proliferative effect of HIIT on the endometrium of women with EC by comparing endometrial biopsy samples of patients

before undergoing a HIIT intervention to their post-HIIT endometrial tissue/hysterectomy specimens.

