# 2.2 Exploratory Objectives

# 3.0 STUDY ENDPOINTS

# 3.1 Primary Endpoints

3.1.1 Change in Ki-67 proliferation values within HIIT intervention group between initial biopsy and surgical biopsy

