whether obtained at UNC-CH or at a referring institution, will be available for analysis in this study. The preferred treatment management for women with EC and CAH is surgical staging, which includes total hysterectomy, bilateral salpingo-oophorectomy, and lymph node assessment. Once enrolled on this pre-operative window study, patients will undergo baseline physiological testing to determine peak cardiorespiratory fitness (VO2peak) and maximum heart rate (HR). This physiological testing will then be used to construct an individualized HIIT intervention, consisting of 4 to 8 at-home training sessions, which will be completed prior to surgical staging. The effect of HIIT will be compared between pretreatment endometrial biopsies and their corresponding post-treatment hysterectomy specimens, with proliferation (i.e. Ki-67 staining) as the primary endpoint of interest. In addition, enrolled patients will undergo repeat endometrial biopsy post-HIIT intervention at the time of their surgical staging; this is being done to ensure that we are accurately evaluating the effects of the HIIT intervention on the endometrial tumors themselves and not differences found due to the type of specimen examined (i.e. endometrial biopsy specimen obtained in clinic versus hysterectomy specimen obtained at the time of surgery). Thus, we plan to compare pre-treatment endometrial biopsies to both post-treatment endometrial biopsies and hysterectomy specimens. Efficacy, tolerability, adherence, and exercise enjoyment will be assessed before and after the intervention as secondary outcomes. All women enrolled will receive a \$100 gift card for participating in this study.

[figure not shown]
Potential prospective subjects will be identified in the following ways: study staff may review the medical records of patients listed on the clinic schedule to determine if a patient meets eligibility criteria for this research study prior to the patient meeting with the physician. Alternatively, patients may be referred to the research team by their UNC physician, outside physician, self-refer or may be discussed at disease specific conferences. In all cases, a member of the research team will review the medical record to see if the patient meets basic eligibility criteria. The patient's physician will present options to the patient and, if the patient is interested, the research study coordinator will consent the patient and HIPAA authorization will be sought.

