# 8.2 Sample Size and Accrual

The original sample size description: Based on data from our previous studies, we expect a difference of 13% (SD = 14%) for pre-post change in Ki-67 proliferation, and a difference of 1.7 (SD = 1.8) ml·kg·min for pre-post change in VO2peak, and attrition not greater than 10%. Under these assumptions, having 22 (20 evaluable) subjects per arm would detect the expected differences in both primary endpoints with at least 75% power and 2-sided  $\alpha$ =0.025 (Bonferroni adjustment).

The updated sample size description: Based on data from our previous studies,  we expect a difference of 10.3% (SD = 14%) for pre-post change in Ki-67 proliferation, and a difference of 1.8 (SD = 2.5) ml·kg·min for pre-post change in VO2peak in the HIIT arm, and attrition not greater than 10%. Historically, the pre-post change in Ki-67 and in VO2peak under usual care are 0. Under these assumptions, having 20 evaluable subjects in the HIIT arm would detect the expected differences in both primary endpoints with at least 80% power and 2-sided  $\alpha$ =0.025 (Bonferroni adjustment).

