# **Data Analysis Plans**

The original data analysis plan: Appropriate descriptive statistics for relevant variables (e.g., Ki-67 proliferation, VO2peak, p-mTOR expression, time to exhaustion, etc.) will be calculated by arm and by time (baseline and week 3). For pre-post changes of Ki-67 and VO2peak, the two primary endpoints (and similarly for other variables), differences between groups (HIIT vs. no-HIIT) in Ki-67 (or VO2peak) will be analyzed using analysis of covariance (ANCOVA) with baseline Ki-67 (or VO2peak) used as the covariate.

Our primary analysis will follow the intent-to-treat (ITT) principle, like for many randomized clinical trials. For the primary analysis, we will use a conservative (but valid) approach, and only include key covariates like baseline Ki67 level, stratification factors, in addition to HIIT (treatment assignment). In the exploratory

analysis, we will include adherence and other covariates in the model. Findings from exploratory analysis will be used for hypothesis generation.

The updated data analysis plan: Appropriate descriptive statistics for relevant variables (e.g., Ki-67 proliferation, VO2peak, p-mTOR expression, time to exhaustion, etc.) will be calculated by arm and by time (baseline and week 3).

Our primary analysis will be on pre-post changes in Ki-67 and VO2peak for patients in the HIIT arm and to test whether the differences were significantly different from 0 using Wilcoxon signed rank test.

For now, there are 10 patients randomized to the usual care arm have completed the study. To make good use of the data, we will conduct an exploratory analysis to compare the differences between groups (HIIT vs. no-HIIT) in Ki-67 (or VO2peak), which will be analyzed using analysis of covariance (ANCOVA) with baseline Ki-67 (or VO2peak) used as the covariate (we will also conduct similar exploratory analyses for other variables). We may also include adherence and other covariates in the model. Findings from exploratory analysis will be used for hypothesis generation.

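### Section 8.2 powers and tests VO2peak change as a second primary endpoint, but 2.1, 3.1 and 5.3 name only Ki-67, and the only follow-up VO2peak is optional and post-surgical, so its test against 0 cannot isolate HIIT

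*Combined protocol and SAP*

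**What the plan says.** **Primary endpoint.** Section 2.1 has a single primary objective, on proliferation: "Determine the anti-proliferative effect of HIIT on the endometrium of women with EC by comparing endometrial biopsy samples of patients" before HIIT with their tissue afterwards. Section 3.1 has a single primary endpoint: "Change in Ki-67 proliferation values within HIIT intervention group between initial biopsy and surgical biopsy". Section 5.3 describes Ki-67 staining "as the primary endpoint of interest".

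**Sample size and analysis.** The updated text of 8.2 states that 20 evaluable HIIT patients "would detect the expected differences in both primary endpoints with at least 80% power", at a Bonferroni two-sided 0.025. It assumes a VO2peak change of 1.8 (SD 2.5) ml/kg/min and a Ki-67 change of 10.3 (SD 14) percentage points, and says that the historical changes "under usual care are 0". The updated primary analysis takes the pre-post changes in both Ki-67 and VO2peak "to test whether the differences were significantly different from 0 using Wilcoxon signed rank test". Descriptive time points are given as baseline and week 3.

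**Schedule.** The Time and Events Table (6.1) marks VO2peak at baseline and at the post-surgical visit only. On timing, footnote 4 of the schema (5.1) says: "Post-surgical testing and SOC post-surgical visit will take place 2-4 weeks after SOC surgery". That footnote and footnote 3 of the table both make the second VO2peak test optional. Section 5.3.5 calls the second measurement post-HIIT.

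**Accrual stop.** Section 8.1 continues accrual to 20 evaluable HIIT patients, meaning complete data before and after HIIT. It does not say whether the optional VO2peak is part of complete data.

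**The concern.** Two things are wrong together. First, the statistical section has a primary endpoint that the objectives and endpoints sections do not list, and Ki-67 gives up half its alpha to it. Second, if 8.2 is carried out on the scheduled data, the VO2peak test does not answer the question put to it. No VO2peak test is scheduled between the last HIIT session and surgery, so the interval from baseline contains HIIT, a hysterectomy and 2 to 4 weeks of recovery. A null or negative result could not be read as absence of a HIIT effect, yet it would be reported as a primary result.

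The meaning of *evaluable* matters separately because it decides when accrual stops. If the optional VO2peak counts, the 20 are selected on accepting an optional test, and accrual continues past 20 women with paired Ki-67. If it does not count, nothing supports n=20 for VO2peak.

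**Working it through.** **Inputs (updated 8.2).** VO2peak change 1.8, SD 2.5, d = 1.8/2.5 = 0.72. Ki-67 change 10.3, SD 14, d = 10.3/14 = 0.736. n = 20, two-sided alpha 0.025 each (z = 2.241), attrition at most 10%. Uptake of the optional test and any effect of surgery on VO2peak are not given; the values used for them below are assumptions.

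**1. The plan's own figure.** Paired-change normal approximation: power = Phi(d x sqrt(n) - z).
- VO2peak: 0.72 x 4.472 - 2.241 = 0.979, power 84%.
- Ki-67: 0.736 x 4.472 - 2.241 = 1.049, power 85%.
- Pairs needed for 80% on VO2peak: (2.241 + 0.842)^2 / 0.72^2 = 18.3, so 19.

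The stated minimum of 80% therefore reproduces by this approximation, with one VO2peak pair to spare.

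**2. The named test.** Exact Wilcoxon signed-rank critical values at n=20 (attained size 0.024), with normally distributed changes simulated, give about 75% for VO2peak and 77% for Ki-67. This gap has nothing to do with timing or uptake.

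**3. Fewer tested, or a surgical decrement (both assumed; true HIIT gain 1.8).**

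| Scenario for VO2peak | Normal | Exact Wilcoxon |
|---|---|---|
| 20 pairs, no surgical effect | 84% | 75% |
| 16 pairs | 74% | 64% |
| 14 pairs | 67% | 56% |
| 10 pairs | 51% | 33% |
| 20 pairs, decrement 0.5 | 53% | 45% |
| 20 pairs, decrement 1.0 | 21% | 17% |

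Example: with a decrement of 1.0 the net change is 0.8, and (0.8/2.5) x 4.472 - 2.241 = -0.810, which gives 21%.

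**4. No HIIT effect at all.** If surgery and recovery alone lower VO2peak by an assumed 1.0, the exact test at n=20 rejects 0 in about 27% of trials, essentially always as a fall. By symmetry, a rise of 1.0 unrelated to HIIT would be declared a gain equally often.

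**5. Enrolment if evaluable includes VO2peak.** Attrition alone: 20/0.9 = 22.2, so 23. With an assumed 30% opt-out as well: 20/(0.9 x 0.7) = 31.7, so 32. With 50%: 20/(0.9 x 0.5) = 44.4, so 45.

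**6. Ki-67 alone.** At two-sided 0.05: 0.736 x 4.472 - 1.960 = 1.330, power 91% by normal approximation and about 86% by exact Wilcoxon. At 0.025 the figures are 85% and about 77%.

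**7. Time labels.** Section 5.1 puts HIIT at about 2 to 3 weeks, and the visit is 2 to 4 weeks after surgery. Even if surgery follows HIIT directly, the visit falls at about week 4 (2 + 2) to week 7 (3 + 4). It cannot be the week 3 of 8.2.

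**8. What an estimate would offer.** The 95% half-width for VO2peak change is t x 2.5/sqrt(n): 1.17, 1.44 and 1.79 ml/kg/min for 20, 14 and 10 tested. For 20 HIIT against 10 usual-care patients, unadjusted with the same SD, it is 2.048 x 2.5 x sqrt(1/20 + 1/10) = 1.98, wider than the expected 1.8.

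**The case against.** The strongest defence is the historical usual-care change of 0. If it had been measured over the same pre- to post-operative interval, testing against 0 would be reasonable. The documents do not show this. The statement has no citation of its own, and the two references attached to the planning figures are, by title, a metformin window trial and a sample-size methods paper. The VO2peak figure in 1.2 comes from 3 weeks of HIIT in adults aged 20 to 50, with no surgery mentioned. Titles of unseen references support only *not shown*, not *wrong*.

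Uptake may also be good: 5.2 says that post-testing occurs for all subjects, and 4.1.8 requires agreement to a post-surgery visit. That secures attendance, but both footnotes exempt VO2peak specifically. The usual-care patients could help to separate surgery from HIIT, but 8.2 keeps that ANCOVA exploratory and does not say how many of the 10 had the post-surgical test.

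A reader might infer from the amendment log that VO2peak was deliberately dropped as primary. The log records that a second primary endpoint was removed from 3.1.2 but does not name it. It may have been a between-arm comparison lost with the control arm, and the same amendment updated 8.2, whose current text carries new VO2peak planning figures. The log is not evidence either way. The text under 2.2 is not visible in the copy reviewed, so nothing is claimed about exploratory status; a listing there would not remove the conflict between 3.1 and 8.2.

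**Conclusion.** The point stands on the current text. Section 8.2 disagrees with 2.1, 3.1 and 5.3 on whether VO2peak is primary, and the scheduled VO2peak data cannot support the test that 8.2 describes. The week 3 label and the definition of evaluable also need reconciling.

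The power loss rests on assumed uptake and an assumed surgical effect. Without either, exact VO2peak power is already about 75%; the scenarios above take it from 64% down to 17%.

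Four stronger readings are not supported:
- *The 80% claim is an arithmetic error.* It reproduces by normal approximation; it falls short only for the Wilcoxon test that the plan names.
- *Surgery biases VO2peak downward.* The documents give neither size nor direction. If surgery does lower it, a significant rise would still be informative.
- *The split alpha inflates error.* Using 0.025 for Ki-67 only costs power.
- *The Ki-67 result is compromised.* Its post-treatment tissue is taken at surgery, so VO2peak timing does not touch it.

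**What to change.** 1. In 8.2, make Ki-67 the only primary endpoint, in line with 2.1 and 3.1, and restate its power at n=20 for the planned Wilcoxon test: about 77% at two-sided 0.025. If the sponsor drops the Bonferroni split, fix 0.05 (about 86%) by amendment before any Ki-67 result is analysed.
2. Report VO2peak as an exploratory baseline-to-post-surgery change with a 95% confidence interval and the number tested, not as a test of HIIT against 0. Keep the ANCOVA with the usual-care patients exploratory, as already planned, and state how many of them had the same post-surgical test.
3. In 8.1, define evaluable for the accrual stop as paired Ki-67. Sections 2.1, 3.1, 5.3 and 8.1 word the post-HIIT specimen differently: 3.1 names the surgical biopsy, 5.3 links the primary endpoint to the hysterectomy specimen and adds that "we plan to compare pre-treatment endometrial biopsies to both post-treatment endometrial biopsies and hysterectomy specimens", and 2.1 and 8.1 allow either. The sponsor should name the specimen before analysis; this review does not choose.
4. Reconcile week 3 in 8.2 and the post-HIIT label in 5.3.5 with the post-surgical visit in 5.1 and 6.1.

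The cost is one protocol amendment with IRB approval before implementation (9.5). No visit or procedure is added. The sponsor gives up a confirmatory fitness claim that this design cannot support.

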# 5.2 Duration of Study

This study will last approximately 10 weeks total. During a SOC visit, subjects will be consented prior to hysterectomy. HIIT exercise will be a home-based program in the intervening weeks between SOC clinic visit and SOC surgery. Subjects can undergo baseline testing on the day of their SOC appointment in the North Carolina Cancer Hospital, or return to an exercise physiology lab in Fetzer Hall after their consent visit. All subjects will be directed to complete 4 to 8 sessions of the at home exercise program, log exercise in study website, and sync Fitbit data. At SOC surgery, endometrial biopsy and hysterectomy specimens will be collected. At a SOC post-operative appointment, 2 to 4 weeks post-surgery, post-testing will occur for all subjects.

# 5.3 Study Details

Obese and overweight (BMI≥25-55 kg/m²) women with type I EC (endometrioid histology) and complex atypical hyperplasia (CAH) will be recruited from the Gynecologic Oncology clinic at UNC-CH. The Division of Gynecologic Oncology at UNC-CH of which [name] is a member has 10 clinically active gynecologic oncologists who care for and treat about 250 women per year with newly diagnosed EC. Obesity rates among the EC patients treated at UNC are approximately 62%, with most of remaining women being overweight. Thus, recruitment to this clinical trial should be successful in 12-18 months. Our previous reported phase 0 clinical trial of metformin easily recruited 20 patients in 12 months.

Women with endometrial cancer or complex atypical hyperplasia are usually diagnosed by endometrial biopsy either obtained in the office using a pipelle device or in the operating room by dilation and curettage (D&C). Our standard practice for outside endometrial biopsies is to obtain the blocks and have the biopsies reviewed by the pathologists at UNC-CH for confirmation of diagnosis. Therefore, all pre-operative endometrial biopsies,

whether obtained at UNC-CH or at a referring institution, will be available for analysis in this study. The preferred treatment management for women with EC and CAH is surgical staging, which includes total hysterectomy, bilateral salpingo-oophorectomy, and lymph node assessment. Once enrolled on this pre-operative window study, patients will undergo baseline physiological testing to determine peak cardiorespiratory fitness (VO2peak) and maximum heart rate (HR). This physiological testing will then be used to construct an individualized HIIT intervention, consisting of 4 to 8 at-home training sessions, which will be completed prior to surgical staging. The effect of HIIT will be compared between pretreatment endometrial biopsies and their corresponding post-treatment hysterectomy specimens, with proliferation (i.e. Ki-67 staining) as the primary endpoint of interest. In addition, enrolled patients will undergo repeat endometrial biopsy post-HIIT intervention at the time of their surgical staging; this is being done to ensure that we are accurately evaluating the effects of the HIIT intervention on the endometrial tumors themselves and not differences found due to the type of specimen examined (i.e. endometrial biopsy specimen obtained in clinic versus hysterectomy specimen obtained at the time of surgery). Thus, we plan to compare pre-treatment endometrial biopsies to both post-treatment endometrial biopsies and hysterectomy specimens. Efficacy, tolerability, adherence, and exercise enjoyment will be assessed before and after the intervention as secondary outcomes. All women enrolled will receive a \$100 gift card for participating in this study.

[figure not shown]
Potential prospective subjects will be identified in the following ways: study staff may review the medical records of patients listed on the clinic schedule to determine if a patient meets eligibility criteria for this research study prior to the patient meeting with the physician. Alternatively, patients may be referred to the research team by their UNC physician, outside physician, self-refer or may be discussed at disease specific conferences. In all cases, a member of the research team will review the medical record to see if the patient meets basic eligibility criteria. The patient's physician will present options to the patient and, if the patient is interested, the research study coordinator will consent the patient and HIPAA authorization will be sought.

Potential prospective subjects will be seen in private clinic rooms by the physician and the team member that will be informing and consenting the subject. The purpose of this study and the risks and side effects of HIIT therapy will be addressed in the consent and verbally explained to the patients. The purpose of serum and tissue collection and the risk to these procedures will be verbally explained to the patients. Informed consent will be obtained from the patients by the study coordinator.

In order to ensure retention of subjects during the proposed HIIT intervention, subjects will be contacted weekly by study staff. These scheduled calls or text messages will ensure that the subjects have no questions about the intervention, that they are tolerating HIIT without any significant adverse effects, that they are syncing their Fitbits, and to make sure they are logging in their exercises on the website every time they work out. Furthermore, subjects will be provided multiple contact numbers for study personnel to contact with questions or concerns about the HIIT intervention (day or night).

After women have undergone hysterectomy/surgical staging for EC or CAH, their corresponding pre-treatment endometrial biopsies and post-treatment endometrial tissue/hysterectomy specimens will be obtained for comparison. Hysterectomy/tumor and repeat endometrial biopsy specimens from the EC and CAH patients in the operating room will be collected via the Tissue Procurement Core Facility (TPF) at the Lineberger Comprehensive Cancer Center (LCCC). In addition, the pre-operative endometrial biopsy slides and blocks will be obtained from referring physicians of these patients for analysis in this study. All patients would have had an endometrial biopsy performed prior to referral to the Gynecologic Oncology clinic as part of their diagnosis of endometrial cancer or complex atypical hyperplasia. Blood (10mL) and urine will be collected pre- and post-HIIT intervention for metabolomic profiling as a strategy to identify other potential biomarkers of response to HIIT. Fresh EC tissue will be collected post-HIIT intervention via hysterectomy for metabolomic profiling and correlation with metabolic changes in serum. These biospecimens will be stored indefinitely for research purposes unless the participant refuses to agree to storage for future use on the informed consent form.

HIIT Intervention: **Following** the VO2peak testing, patients will be provided with a FitBit HR2+ wristband accelerometer to track heart rate training zone and view their physical activity throughout the study. Patients will be counseled by the study exercise physiologist (PI, [name]) to discuss available local training resources (e.g. walking, jogging, aerobic exercise equipment) depending on individual patient lifestyle and preferences (Fig 4). The selected exercise-training mode for each patient will be used for that patient's HIIT

**Figure 4.** Schematic of HIIT intervention in a randomized phase 0 trial in obese EC patients.

throughout the study. Patients will be instructed on how to achieve their individual prescribed training zone [85-95% maximal heart rate (MHR)] that will be calculated based on VO2peak assessment and pre-programed into the wrist monitor. Participants will be asked to undergo 4 to 8 sessions of home-based interval fitness bouts. The exercise will consist of a 5-min warm-up, followed by 10 1-min intervals at 85-95% MHR within each bout, separated by 1-min low intensity (50% MHR) or complete rest. Participants will document each interval session by electronically logging data into the study website (exercisenutritionasmedicine.com) on the CHAI-core web platform. They will be emailed information to login to the website. This site will automatically upload activity data from the FitBit, as well as provide reminders to complete HIIT and display HR goals. The site will also be used to send text messages reminding participants to track and complete their exercise, charge and sync their FitBits, and to aim for their target HR. This messaging will not include any protected health information and standard messaging rates will apply. During this same visit, total body composition and visceral fat will be assessed using brightness-mode ultrasound (Logiq-e, GE Healthcare, Wisconsin, USA) as previously validated.

